9.2. Timing

Participants will undergo screening and, once the HSV-2 infection is confirmed, baseline visits, and then follow-up visits at 14, and 28 after baseline, in addition there will be a follow-up call after 2-5 days after the baseline visit.

9.3. Analysis Sets

The *As Treated (AT) Population* will consist of all participants that were enrolled in the trial and that applied VIBLOK at least once.

The *Per Protocol (PP) Population* will consist of all participants who fulfil the protocol in the terms of the eligibility and that applied VIBLOK for at least 26 days.

The primary and secondary endpoints will be reported based on the AT population.

Descriptive and summary statistical analysis will also be performed on all primary and secondary endpoints on the PP population.

Prior to final statistical analysis, designated staff will develop a memo that describes the exclusions from analysis populations.

9.4. Missing Data

All possible steps will be taken to minimize missing data in the study, including monitoring of data forms for completeness and efforts to track and maintain contact with study participants during the follow-up period. Missing data will not be imputed and the data will be analyzed as is. An investigation may be made concerning the sensitivity of the results of analysis to the method of handling missing values, especially if the number of missing values is substantial.

9.5. Endpoints

9.5.1. Primary Endpoint

The primary endpoint for this clinical study is SADE incidence after minimally 26 days of VIBLOK treatment in the AT population. This analysis will be repeated for the PP population.

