9.1. Sample Size Determination

The primary endpoint is the SADE incidence at 28 days of VIBLOK usage.

With a sample size of 36, an exact two-sided 95.0% confidence interval for a single proportion will show that the SADE incidence is below 10% at an expected incidence of 0.1%. Taking into account a drop-out rate of 15%, the estimated sample size needed is 42 study participants applying the VIBLOK cream.

The secondary endpoint is VIBLOK performance.

Statistical analysis will evaluate whether the disagreement rate in positivity between the pre- and post-treatment swabs is indicative of a decrease in detection frequency. For each person, the number of swabs on which shedding occurs only pre-intervention will be assessed, and then the number of swabs on which shedding occurs only post-intervention will be subtracted. If this number averages above zero, it indicates that the detection rate is decreased following intervention, and therefore a protective effect of the intervention with regard to shedding. Since this number is not distributed according to a known distribution, we will compare it to zero using a non-parametric test, the Wilcoxon signed-rank test. With an 8% anticipated asymptomatic shedding rate, 80% power and type I error of 5%, 40 participants taking samples for 28 days are needed to show a 50% reduction post-intervention, i.e. after applying VIBLOK.

Taking into account a drop-out rate of 15%, up to 46 adults applying VIBLOK cream are needed.

Total number of subjects to be enrolled.

Taking into account an overall screenfailure rate of 45% for absence of a confirmed HSV-2 infection, up to 84 subjects will be enrolled to get to the required minimum of 46 adults applying VIBLOK.

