### 1.3 Statistical hypotheses

#### Primary endpoint

SADE incidence after minimally 26 days of VIBLOK treatment, will be assessed by calculating the upper limit of the two-sided exact 95% Clopper-Pearson confidence interval which needs to be below 10%.

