#### **2.5.4 Safety Analysis Set**

The Safety Analysis Set will include all participants from the As Treated Population who provided safety data.

It is assumed that all participants applying VIBLOK at least once are included in the safety analysis; if that is not so, an explanation will be provided.

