### 5.2 Adverse Events

#### 5.2.1 Primary endpoint

The primary endpoint of this study is a safety endpoint:

The number of Serious Adverse Device Effects during minimally 26 days of VIBLOK use. A two-sided exact 95% Clopper-Pearson confidence interval will be calculated. The study will be considered a success in case the upper limit of the 95% confidence interval is below 10%.

The analysis will be based on the As Treated Population and repeated for the Per Protocol Population.

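### The primary success rule counts treated participants lost before day 26 as full event-free observations, while the endpoint and the sample size assume 26 days of follow-up.

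*Protocol*

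**What the plan says.** Protocol 9.5.1 gives the primary endpoint as "SADE incidence after minimally 26 days of VIBLOK treatment in the AT population". The As Treated set, in Protocol 9.3 and SAP 2.5.2, is "all participants that were enrolled in the trial and that applied VIBLOK at least once"; no length of follow-up is required.

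SAP 1.3 assesses the endpoint by "calculating the upper limit of the two-sided exact 95% Clopper-Pearson confidence interval which needs to be below 10" per cent. SAP 5.2.1 turns this into the trial verdict and adds: "The analysis will be based on the As Treated Population and repeated for the Per Protocol Population". No decision rule is attached to the Per Protocol repeat.

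Three other rules bear on the denominator. Protocol 5.3.1 keeps early discontinuers in the analysis and does not replace them. Protocol 9.4 and SAP 2.3 rule out imputation. SAP 2.9 leaves the handling of drop-outs to a separate data-handling plan that is not among the documents.

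On sample size, Protocol 9.1 and SAP 1.4 start from 36 participants and continue: "Taking into account a drop-out rate of 15%, the estimated sample size needed is 42 study participants applying the VIBLOK cream". The secondary endpoint then raises the number treated to 46.

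**The concern.** The endpoint claims something about incidence over at least 26 days, but the denominator requires only one application. Under the stated rules, a participant who applies the cream a few times and is then lost, with no SADE on record, counts as much as one observed to day 28.

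The sizing takes the other view. Raising 36 to 42 makes sense only if drop-outs give no information. The analysis then credits each of them with full information, so the upper limit does not widen as follow-up is lost.

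At stake is a statement, meant to support CE marking, that SADE incidence is below 10%. It could rest on fewer participants of known 26-day status than the plan's own calculation requires.

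**Working it through.** **Inputs.** Two-sided exact 95% interval with a 10% margin (SAP 1.3, 5.2.1); 36 needed, 15% drop-out, 42 for the primary endpoint, 46 treated, expected incidence 0.1% (Protocol 9.1).

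**Formula.** With no events the Clopper-Pearson upper limit is U(0, n) = 1 − 0.025^(1/n). With x events it is the 97.5th percentile of Beta(x + 1, n − x).

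**1. The plan's own figure.**
- U(0, 36) = 1 − 0.025^(1/36) = 9.74%, below 10%.
- U(0, 35) = 1 − 0.025^(1/35) = 10.003%, not below 10%.

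So 36 is exactly the smallest number that passes with no SADEs. At 0.1% incidence the chance of none in 36 is 0.999^36 = 96.5%.

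**2. Drop-out.** 36 × 1.15 = 41.4, which rounds up to the stated 42 (36/0.85 = 42.4 would round up to 43). Either way drop-outs are taken to contribute nothing. Of 46 treated, 46 × 0.85 = 39.1 remain, about 39.

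**3. The two limits with no recorded SADE.** Known status means that SADE status is known through day 26.

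| Treated | Unknown status | Known status | As Treated limit | Known-status limit |
|---|---|---|---|---|
| 46 | 0 | 46 | 7.71% | 7.71% |
| 46 | 7 (15%) | 39 | 7.71% | 9.03% |
| 46 | 10 (22%) | 36 | 7.71% | 9.74% |
| 46 | 11 (24%) | 35 | 7.71% | 10.003% |
| 46 | 16 (35%) | 30 | 7.71% | 11.57% |
| 42 | 6 (14%) | 36 | 8.41% | 9.74% |
| 42 | 7 (17%) | 35 | 8.41% | 10.003% |

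The row with 16 unknown is illustrative; the documents give no such rate.

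**4. How likely the verdicts are to part.** Assume that every drop-out is of unknown status and that losses are independent. The binomial chance of at least 11 of 46 lost is 7% at the planned 15%, 31% at 20% and 62% at 25%; the last two rates are assumptions. For at least 7 of 42 at 15% it is 45%.

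**5. One unseen event.** U(1, 46) = 11.53%, which fails; 54 participants would be needed to pass with one SADE. At 46 treated, success therefore requires none, and one unrecorded SADE in a lost participant would change the verdict.

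**6. Chance of a false success.** Suppose the true 26-day risk is 10% and lost participants contribute no recorded events. The chance of seeing none in k observed participants is 0.9^k: 0.8% for 46, 2.5% for 35, 4.2% for 30 and 12.2% for 20. The nominal upper-tail level is 2.5%, so the error rate exceeds it materially only when known status falls well below 36.

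**The case against.** An all-exposed denominator is a usual choice for safety, and the Synopsis words the primary endpoint as incidence over the period of use, which such a denominator fits. That stands. The mismatch arises from the 26-day wording in Protocol 9.5.1 and SAP 1.3, and the documents also use a 28-day version in Protocol 9.1 and SAP 1.4. The varying time frame is part of the fault.

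No sentence says that lost participants are counted as SADE-free. It follows from the As Treated denominator, the inclusion of early discontinuers and the absence of imputation. Dropping such people from the denominator would conflict with those rules. The separate data-handling plan may say more, but the success rule should be readable from the SAP.

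Three stronger readings are tempting, and the documents do not support them:

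- A reader might infer that participants with no safety data will swell the denominator. SAP 2.5.4 does define a set for this case ("The Safety Analysis Set will include all participants from the As Treated Population who provided safety data") that the primary analysis does not use. But first application is supervised on site at a visit with an adverse event assessment (Protocol 5.2.3), and SAP 2.5.4 expects every treated participant to be covered and promises an explanation otherwise. The case should be rare.
- A reader might equate every drop-out with unknown status. Protocol 5.3 and 5.3.1 require repeated contact attempts, a letter and renewed efforts for safety purposes, and ask permission to follow those who withdraw over device safety. Unknown status is a subset of drop-out.
- A reader might conclude that heavy loss would stay hidden. The Per Protocol interval is reported, exposure is summarised (SAP 5.1) and each discontinuation is listed with its duration of use (SAP 3.1).

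None of these safeguards enters the verdict, however. The Per Protocol repeat carries no decision rule, and because it requires 26 days of application it would remove someone who stopped early because of a SADE. The missing-data sensitivity analysis is optional, with no method named.

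**Conclusion.** The point holds as a gap between the endpoint, the sizing and the success rule. With no SADEs, the As Treated limit passes at 7.71% of 46 whatever the follow-up, while the 26-day claim needs 36 participants of known status. The verdicts part at 11 of 46 with unknown status (24%), or at 7 of 42 (17%), the number the plan calls sufficient for this endpoint.

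The documents do not support saying that the planned trial would reach a wrong verdict. At 15% drop-out from 46, even with every drop-out of unknown status, 39 remain and the limit of 9.03% passes. The risk arises when loss exceeds plan. Mandatory exit after a second recurrence (Protocol 5.2.6), in people with at least three recurrences in a year, is one further source of early exit.

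The conclusion assumes that the rules are applied as written and that participants of unknown status give no information. The second assumption is pessimistic, since part of their period was observed.

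**What to change.** In Protocol 9.5.1 and SAP 1.3 and 5.2.1:

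1. Use one time frame for the primary endpoint, and align the Synopsis, Protocol 3.1 and 9.1 and SAP 1.4 with it. Say whether it counts days since Visit 1 or days of use, since the two can differ when a recurrence interrupts use (Protocol 5.2.6).
2. State how As Treated participants without follow-up to day 26 are counted.
3. Keep the As Treated interval. Declare success only if the exact upper limit is also below 10% among participants who had a SADE at any time or whose SADE status is known through at least day 26, on or off cream.
4. Report the number with unknown status.

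The second set keeps early SADEs but drops event-free losses, so it leans conservative. That is why it is better added as a condition than used to replace As Treated. The cost is wording and one extra interval. The limit that decides becomes less favourable: about 9.0% instead of 7.7% at the planned drop-out with no SADEs, which still passes.

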9.5.2. Secondary Endpoints

Secondary endpoints with respect to device performance are:

- Within-participant HSV-2 DNA detection rate on days with asymptomatic shedding
- HSV-2 copy number on HSV DNA positive samples detected by quantitative real-time PCR on days with asymptomatic shedding

The secondary endpoint with respect to safety is:

- Total number and type of AEs after minimally 26 days of VIBLOK use.

Secondary analyses will be performed in the AT population. The analyses will be repeated for the PP population.

9.5.3. Exploratory Endpoints

Subanalyses will be performed as follows:

- To explore VIBLOK's blocking ability in relation to
 - Gender
 - Time between VIBLOK application and sampling
 - Shaving and waxing habits
- Participant satisfaction using VIBLOK as assessed on the participant questionnaire

Exploratory analyses will be performed in the AT population. These analyses will not be repeated for the PP population.

9.6. Endpoint Analysis

All statistical analyses will be performed by CLJI or a designee. Participant data listings and tabular and graphical presentations of results will be provided. All clinically relevant baseline and follow-up variables will be tabulated. Descriptive statistics will be used for continuous variables (e.g., mean, standard deviation, sample size, minimum, and maximum) and frequency tables or proportions for discrete variables.

Swab samples will be analyzed by a core laboratory for HSV DNA and the mean HSV-2 copy number on HSV-2 DNA positive samples.

Further details of the statistical methods will be provided in the Statistical Analysis Plan.

10. Study Administration

10.1. General Study Organization

CLJI Worldwide is the Study Sponsor, and has the overall responsibility for the conduct of the study, including assurance that the study meets the regulatory requirements of the appropriate regulatory bodies. The Sponsor will have certain direct responsibilities and will coordinate other responsibilities to the specified committees, core labs and other support services as necessary.

CLJI Worldwide will be responsible for submitting the Investigational Plan and all changes to it to the national competent authority and local EC to obtain ongoing approvals as needed.

CLJI Worldwide and Core Laboratories will maintain copies of correspondence, data, shipment of devices, adverse device effects and other records related to the clinical trial as appropriate.

CLJI Worldwide will submit all reports required by the appropriate regulatory authorities as identified in this section of the regulation. This may include unanticipated and serious adverse device effects, withdrawal of EC approval, current investigators list, annual progress reports, recall information, final reports and protocol violations.

10.2. Steering Committee

The Steering Committee will be responsible for general oversight of the trial. This committee will meet periodically to monitor clinical site progress, and protocol compliance. This committee will be responsible for reviewing the final results, determining the methods of presentation and publication, and selection of secondary projects and publications. The committee will be comprised but not limited of [name], [name], [name], and [name] with at least one of the medical doctors (MD) being a study investigator.

10.3. Data Monitoring Committee

The Data Monitoring Committee (DMC, also known as the Data Safety Monitoring Board, DSMB) will consist of at least 3 members, with minimally one member independent from the Sponsor, the investigators, or anyone involved in the clinical care of the study participants. (S)he will not have scientific, financial, or other conflict of interest related to the Sponsor or the investigators.

The DMC committee will review all safety data and will monitor the rates of SAEs, device and procedure failures, and any device-related adverse events from this clinical study and make recommendations based upon the safety analyses. It will also be responsible for the developing a charter and deciding on early termination of the trial as necessary. The frequency of the DMC meetings will be determined prior to study commencement; however, the DMC may call a meeting at any time if there is reason to suspect safety is an issue. DMC oversight for this trial is expected to be rigorous with frequent review of all essential safety data.

10.4. Core Laboratories

A Core laboratory will be established for the analyses of the swabs, and serology. Standardized protocols for acquiring and transmitting electronic records will be developed and documented prior to study initiation.

10.5. Clinical Sites

CLJI Worldwide will select qualified investigators, ship devices only to participating investigators, obtain a signed Clinical Study Agreement and provide the investigators with the information and training necessary to conduct the study. CLJI Worldwide will retain copies of all study-related correspondence with study sites.

10.6. Site Training

Clinical sites will be chosen that have had experience with patients with viral STIs. Additional training of appropriate clinical site personnel will be the responsibility of the Sponsor. To ensure proper device usage, uniform data collection, and protocol compliance, the Sponsor will present a formal training session to study site personnel which will review the instructions for use of the device, the Investigational Plan, techniques for the identification of eligible patients, instructions on in-hospital data collection, standardized data collection for core laboratory analysis, methods for soliciting data from alternative sources, schedules for follow-up with the study site coordinators, and regulatory requirements. Detailed feedback regarding completion of forms will be provided by the Sponsor, and through regular site monitoring. The sponsor reserves the right to enforce retraining for sites who have demonstrated study or procedure compliance issues.

10.7. Study Monitoring

CLJI Worldwide, or its designee, will conduct investigational site monitoring to ensure that all investigators are in compliance with the protocol and the Investigator's Agreement, and that all study participants have been properly consented with the current version of the informed consent document. CLJI Worldwide will evaluate circumstances where an investigator deviates from the clinical protocol and will retain the right to remove either the investigator or the investigational site from the study.

Routine on-site monitoring visits shall include verification of the following:

- Compliance with the protocol, any subsequent amendment(s), ISO14155 and maintenance of regulatory requirements; deviations shall be discussed with the principal investigator(s) or authorized designee, documented and reported;
- Only authorized individuals are participating in the clinical investigation;
- The investigational device is being used according to the protocol and instructions for use;

- Investigational site resources, equipment and the investigational site team, remain adequate throughout the duration of the clinical investigation;
- Signed and dated informed consent forms have been obtained from each participant at the point of enrollment or before any clinical-investigation-related procedures are undertaken, using an informed consent form approved by the ethics committee;
- Source documents and other clinical investigational records are accurate, complete, up to date, stored and maintained appropriately;
- CRFs and queries are complete, recorded in a timely manner, and consistent with source documents; (hence the monitor will perform 100% source verification of the inclusion/exclusion criteria, all adverse events and all endpoints. Further, a random sample of at least 10% of the participants (at least 2 participants per site) will be fully source verified);
- All adverse events and device deficiencies are reported to CLJI without unjustified delay;
- All serious adverse events and deviations are reported to the EC, if required;
- The storage and investigational device accountability are correct and the device accountability process is being followed;
- All other required reports, notifications, applications, submissions and correspondence are maintained in the investigator's files and are accurate, complete, timely, legible, dated and identify the clinical investigation;
- Current laboratory normal values, laboratory certifications, accreditations, or other validations are present in the investigator's file;
- Participant withdrawal has been documented; the monitor shall discuss this with the principal investigator or his/her authorized designee;
- Participant non-compliance with the requirements stated in the informed consent has been documented; the monitor shall discuss this with the principal investigator or his/her authorized designee;
- Suitability of the attempts to contact lost to follow-up participants and any intermediaries;
- The principal investigator and investigation site team are informed and knowledgeable of all relevant document updates concerning the clinical investigation, and
- Any corrective and preventive actions, as needed, have been implemented and are effective.

Monitors shall be appropriately qualified per the following requirements:

- Qualified in the field of the applicable regulations and ISO14155:2011 through training and experience as well as scientific or clinical knowledge;
- Knowledgeable on the use of the investigational device(s) and relevant requirements, protocol and informed consent process;
- Trained on the CLJI's clinical quality assurance and quality control system

All monitoring activities shall be documented in a written report. The frequency of monitoring visits will depend on enrollment and center compliance, but each center will at least be visited once per year. Further details are laid out in the monitoring plan.

CLJI Worldwide will review significant new information, including unanticipated adverse events and ensure that such information is provided to the DMC, study investigators and to all reviewing ECs and regulatory agencies as necessary.

Efforts will be made to ensure that data collection compliance is monitored and communicated to the Investigators in a timely manner throughout the trial.

10.8. Data Management

CLJI Worldwide will provide data management through an electronic data capture (EDC) system.

CLJI Worldwide will prepare written progress reports and a final report based on data in the database and will also coordinate with the DMC to ensure data reports are available in a timely manner for all reviews. The core laboratory will be also coordinated by the Sponsor and/or respective vendor so that core lab data for each participant is recorded in the e-CRF.

10.9. Publication Policy

The Study Steering Committee members will plan and review the study publication strategy and review proposed papers and presentations. The committee co-chairmen will develop the format for submission and review of proposed publications. The committee will ensure accuracy of data reporting and will provide editorial assistance and review as needed. Investigators will be required to submit requests for presentation or publication for committee review and approval.

Publication or presentation of the overall clinical study results and/or site specific results of study devices which have not been released, and which still may be undergoing development, requires the prior written approval of CLJI Worldwide. After CLJI Worldwide has had the opportunity to review and comment upon the publication or presentation of the overall clinical and/or site-specific results then Institutions and Investigators will comply with the publication/presentation protocol set forth in the Clinical Study Agreement.

In the event that the multicenter publication has not been completed within one (1) year from the date of the completion or termination of the Study, then notwithstanding the foregoing, the site may individually publish a Proposed Publication regarding its individual results from the Study, provided that the Proposed Publication is first reviewed by Sponsor.

During agreed upon interval and at the conclusion of the trial, a multicenter abstract reporting the primary results will be prepared and presented at a major conference. A multicenter publication will also be prepared for publication in a reputable scientific journal. No publication of results from any single center experience will be allowed until the primary endpoint and secondary endpoints are analyzed, in order to allow for preparation and publication of the multicenter results. The analysis of other pre-specified and non-pre-specified endpoints will be performed by CLJI Worldwide. Additional proposed investigations will require the approval of CLJI Worldwide.

CLJI Worldwide will provide statistical support for the publication process.

11. Ethical & Regulatory Considerations

The VIBLOK cream is not commercially available in any country. The clinical investigation shall be conducted in accordance with the ethical principles that have their origin in the Declaration of Helsinki (as updated in Fortaleza Brazil in 2013) and in compliance with ISO14155:2011 and any regional or national regulations. The clinical investigational plan (including the Investigator's Brochure, protocol, and informed consent document) to study the VIBLOK cream must be reviewed and approved by the appropriate national competent authority and local or regional Ethic Committee (EC) where the clinical investigation is to be

conducted before enrollment of participants may begin. Any additional requirements imposed by the ethics committee or regulatory authority shall be followed.

Changes to the investigational plan that may increase the risk or present new risks to the participant must be approved in writing by CLJI Worldwide, the regulatory authorities and the EC before the change is implemented.

